To be conservative, our sample size estimate is based on an initial estimate of a 43% effect, the weighted average of the 48% reduction effect observed in the Lauterbach study and the 33% reduction effect observed in the Oquendo study. We adjusted for a potential attenuation of the effect due to non-adherence; estimating 15% non-adherence leads to a final estimated effect size of 37%. As discussed below, correction for the loss of data from patients who dropout is addressed through estimates of the sample size requirement, not the effect size for the intervention.

Missing Data from Attrition

In randomized clinical trials, Lauterbach (2008) and Oquendo (2011) reported overall attrition rates of 58% and 50% in the lithium group respectively, of which 21% and 11% were treatment related. Moreover, Lauterbach reported a similar rate of attrition for the placebo group, suggesting that there was no differential dropout.

The proposed study, unlike the previous trials, allows for continued enrollment of subjects who discontinue study medications. The sample size calculations are based on a dropout rate during the course of the study of approximately 40%, or assuming that the dropout rate is uniform, a reduction in the effective sample size of approximately 20%. Allowing for up to 40% dropout or approximately a 20% loss of data for reasons unrelated to treatment, the statistical power calculation is based on an effective sample size of 1,490 evaluable patients from a total of 1,862 enrolled. For the primary time to event analysis, we will censor follow up at the first occurrence of the primary endpoint event, death, or withdrawal from the study for any reason.

We will test the missing at random assumption using a Bayesian Pattern Mixture Missingness approach (Rybin et al., 2013), to validate the results and identify potential bias from possible non-random patterns of missing data. For secondary longitudinal analyses, we will evaluate missingness patterns and perform sensitivity analysis based on multiple imputation methods.

Non-Adherence to Study Protocol

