At the conclusion of the 1-year study treatment, participants will be referred to their treating mental health provider for continued management. There are data to suggest that suicidality and mood disturbances may be increased after stopping lithium. To insure continuity, the appointment with the subject's providers will be scheduled well before completion of the study. The Research Team will maintain responsibility for the subject until they have been seen by their treating clinician in a face-to-face encounter; the goal will be to provide warm-hand-offs through encounters that include the Research Team, the clinical provider, and the patient whenever possible. The research team will ensure that each study participant has a prescribing mental health provider assigned to him/her prior to study Month 10.

At the End of Study visit, the participant and the treating mental health provider will be informed of the treatment assignment. They will be reminded about the possible risks associated with rapid withdrawal of lithium and the need for a slow taper if lithium is to be discontinued. Patients will be asked to return for a 30-day follow-up study visit.

Patients who withdraw consent

Participants withdrawing consent will be asked to participate in a final study assessment. The blind will be broken at the time of this assessment and no further data will be collected. The Research Team will contact the participant's treating mental health provider to recommend gradual tapering of lithium as needed.

Patients who discontinue study treatment prior to 1 year

The investigator may discontinue the study medication for any reason, including adverse effects, safety concerns or protocol violations. In addition, participants may elect to discontinue study medication at any time. Discontinuation of study medication will not automatically result in withdrawal of the participant from the trial, nor unblind the study treatment. The investigators will encourage the participant to continue with study assessments but they will not be required to complete EKGs, blood draws or vital signs except for the 30 day follow-up visit (see Table 7). If a participant does not agree to continue assessments, the blind will be broken, to the participant's mental health provider, at the time they are tapered or discontinued. All ratings and assessments will be completed before the blind is broken.

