3.2. Description of the Intervention Strategy

Eligible patients who consent to participate will be randomized to receive Lithium or placebo. Initial dosage will be 600 mg /day of lithium (or matching placebo), to be titrated to achieve serum lithium level of 0.6 to 0.8 meq/liter. Mock serum lithium level for placebo patients will be calculated using Therapeutic Drug Monitoring method (Yukawa, 1993) based on age, weight, serum creatinine level, adherence, and side-effects. Titration visits will occur at intervals of 5-7 days over 3 months, with maximum allowed dosage not to exceed 1500mg.

Once the target serum lithium level has been reached the patient will be on steady state maintenance phase for the rest of the study with active participation and intervention terminating at 12 months after randomization.

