3.4. Definition of per-Protocol sample

Adherence to allocated intervention will be ascertained for randomized subjects for identification of “per-Protocol” sub-group. Adherence will be determined by pill count for both lithium and placebo groups and additionally, by serum lithium level for the lithium group. These two methods are described below. Those in the lithium intervention group who are adherent to the protocol based on either of the two methods will be considered as adherent. All study subjects, who are adherent to the protocol, will be included in the “per-Protocol” analytic sub-sample.

Method 1: Based on pill count from Form T03 Study Drug Adherence Form data.

Percent adherence for each prescribed dosage will be computed using the following algorithm:

$$\% \text{ adherence} = (\text{Total \#tablets taken} / \text{Total \#tablets prescribed}) * 100\%$$

These percent adherences for each prescribed dosage will be averaged for each patient and those with $\geq 80\%$ overall adherence during the steady state follow up period will be considered adherent to the protocol.

Method 2: Based on target serum lithium level

Study participants in the lithium augmentation group who reach the target serum lithium level of 0.6-0.8 meq/liter during the titration period and maintain within target ± 0.1 meq/liter (i.e., 0.5-0.9 meq/liter) during the entire steady state follow up period will be considered adherent to the protocol.

4. Primary Analysis

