4.5. Sensitivity Analysis

The primary efficacy analysis will be repeated under 3 different scenarios as follows.

- (1) Randomization was stratified on two factors: (1) Bipolar or Major Depressive Disorder diagnosis, and (2) prior history of suicide attempt. Cox Regression Model as described in section 4.3 will be refitted with the inclusion of diagnosis variable and suicide history variable in the model.
- (2) Primary efficacy analysis will be repeated on the “per-Protocol” sample with adherence as defined in section 3.4 to evaluate efficacy among those adherent to the protocol.
- (3) Primary efficacy analysis will be repeated on the modified ITT analytic cohort that excludes all randomized subjects who terminated prior to the first titration visit.

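### The SAP's pill-count rule lets a participant who stopped study drug count as adherent, and the per-protocol analysis then includes that person's off-drug months

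*SAP*

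**What the plan says.** SAP 3.4 offers two routes to adherence.

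- **Method 1 (both arms)** is tablets taken over tablets prescribed, computed for each prescribed dosage. "These percent adherences for each prescribed dosage will be averaged for each patient and those with" 80% or more "overall adherence during the steady state follow up period will be considered adherent to the protocol".
- **Method 2 (lithium only)** requires reaching the target serum level in titration and then staying within 0.5-0.9 meq/liter "during the entire steady state follow up period will be considered adherent to the protocol". SAP 3.2 describes steady state as a "steady state maintenance phase for the rest of the study with active participation and intervention terminating at 12 months after randomization".

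Lithium participants who are adherent "based on either of the two methods will be considered as adherent".

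SAP 4.5(2) repeats the primary analysis on this sample "with adherence as defined in section 3.4 to evaluate efficacy among those adherent to the protocol". In SAP 4.3 the follow-up variable runs from randomisation to the earliest of adjudicated event, death, the 12-month date and last visit or contact.

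Protocol XIV (participants who discontinue study treatment before 1 year) says: "Discontinuation of study medication will not automatically result in withdrawal of the participant from the trial". Protocol VII (Missing Data from Attrition) notes that the trial "allows for continued enrollment of subjects who discontinue study medications". Protocol Table 7 then schedules adherence forms at the early discontinuation visit only, and its lithium-level row is empty.

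**The concern.** Once study drug has been stopped, nothing is prescribed. The off-drug months therefore enter neither the numerator nor the denominator of Method 1, and good pill-taking over a short spell gives the same score as good pill-taking for the full period. The months that the score ignores are still counted as follow-up in 4.5(2).

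That analysis is meant to show efficacy among people who kept to the protocol. Off-drug time in the lithium arm pulls its hazard ratio toward 1. Protocol XII (Discontinuation and Withdrawal) adds that suicide-related behaviour may be more frequent in the first year after lithium is stopped, so the time mixed in may not be neutral. A per-protocol result weakened in this way could be misread as evidence that taking the drug matters less than it does.

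**Working it through.** **1. The plan's own figures.** The stated rates are 15% and 9.45% (SAP 4.3). HR = ln(1 - 0.0945)/ln(1 - 0.15) = 0.611, matching the stated 0.61. Protocol VII obtains its 37% reduction from 43% less 15% non-adherence: 43% x 0.85 = 36.6%.

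**2. What Method 1 returns for someone who stops.** Assumptions: steady state runs from month 2 to month 12, tablets per day are constant, 95% of prescribed tablets are taken while on drug, and drug stops at month m.

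- SAP rule: taken/prescribed = 95%, whatever m is.
- Share of tablets planned to month 12: 0.95 x (m - 2)/10.

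| Drug stopped at month | SAP Method 1 | Share of planned tablets | Off-drug months kept |
|---|---|---|---|
| 4 | 95% | 19% | 8 |
| 6 | 95% | 38% | 6 |
| 9 | 95% | 66.5% | 3 |
| 10 | 95% | 76% | 2 |
| 11 | 95% | 85.5% | 1 |

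**3. Does anything else remove this person?** Stopping drug is not withdrawal (Protocol XIV), so follow-up continues. The follow-up variable has no term for drug stop (SAP 4.3). In the lithium arm, passing Method 1 is enough, so failing Method 2 changes nothing. In the placebo arm Method 1 is the only test.

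**4. Size.** Assumptions: the unattenuated 43% reduction applies on drug, the hazard returns to the placebo rate after stopping, and stops are uniform over months 2 to 12.

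- On-drug lithium rate: 15% x (1 - 0.43) = 8.55%. On-drug HR = ln(1 - 0.0855)/ln(0.85) = 0.550.
- If a share s of the lithium per-protocol group stopped, the off-drug share of time is f = s x 0.5 x 10/12, and HR = 0.550(1 - f) + f.
- s = 10%: f = 0.042, HR = 0.57.
- s = 20%: f = 0.083, HR = 0.587, or about 0.59.

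An exponential mixture with all stops at month 7 gives the same values (0.568 and 0.587). With all stops at month 4 it gives 0.579 and 0.609.

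The 20% comes from Protocol VIII, item C, which allows for up to 20% of subjects discontinuing study medication. That figure covers everyone who stops, including those who would fail the 80% rule or leave the study, so it is an upper-end reading of the share needed here.

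**The case against.** The strongest reply is that the gap is narrow, and much of this reply stands.

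- **Method 2.** A reader might infer that someone who stopped with good earlier levels passes Method 2 as well. The text does not support that: levels must hold over the whole of steady state, which SAP 3.2 runs to month 12. But no levels are drawn after stopping, and the SAP does not say whether absent levels fail the rule or are ignored. It is an ambiguity, not a second route in.
- **Who is affected.** A reader might also infer that everyone who stops counts as adherent. Only those who reached steady state and took at least 80% of tablets prescribed there can qualify. Someone who stops in titration has no steady-state tablets, so the ratio is 0/0 and their status is undefined.
- **Lost contrast.** It is tempting to compare 0.59 with the planned intention-to-treat value of 0.61 and conclude that the per-protocol contrast disappears. That is not like for like, because 0.61 assumes 15% non-adherence. At 20%, the protocol's own attenuation gives 43% x 0.80 = 34.4%, a lithium rate of 9.84% and HR = ln(1 - 0.0984)/ln(0.85) = 0.64. A contrast remains.
- **Larger shares.** The documents do not support 40% or 50% for this group. The trial's 40% is dropout from the study, and those people are censored at last contact. The 50% is one earlier trial's overall discontinuation, and that trial did not retain people off drug in the same way.
- **Reach.** This is one of three sensitivity analyses. The success rule rests on the primary test, and SAP 11 does not list the per-protocol result in its minimum report content.

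None of this changes the Method 1 result. The rule as written admits such people, in both arms.

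**Conclusion.** The point holds for pill-count adherence. A participant in either arm who met the 80% rule in steady state, then stopped study drug and stayed under observation, can enter the 4.5(2) analysis with off-drug months counted. This follows from the stated rules and needs no assumption about rates.

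The size does depend on assumptions. Under those listed, the per-protocol hazard ratio moves from 0.55 to about 0.59 if 20% of the lithium per-protocol group are such stoppers, and to 0.57 if 10% are. If the hazard after stopping lithium exceeded the placebo hazard, the shift would be larger; if few stoppers meet the 80% rule, it would be smaller. The documents give no figure for the actual share.

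A reader might infer that the trial's main conclusion is at risk. It is not: the primary intention-to-treat analysis and the sample size do not use this rule. The change is still worth making, because the defect undermines the stated purpose of the analysis and is cheap to correct.

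**What to change.** - **SAP 4.5(2):** end per-protocol follow-up at the recorded date of permanent study-drug discontinuation, in both arms, if that precedes the other end points. State that this censoring may be informative, since people may stop because they are worsening, and that the result is to be read beside the intention-to-treat analysis.
- **SAP 3.4, Method 2:** state that absent levels after stopping do not count as maintained.
- **SAP 3.4, general:** state that participants who stop before steady state are not per-protocol.

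Replacing the denominator with tablets planned up to month 12 or the primary event is less attractive. Someone with an early event could qualify on a short interval, while an event-free person who stopped later would be excluded, so selection would depend on outcome.

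The cost is SAP wording, a few lines of code and somewhat less per-protocol follow-up. The early discontinuation visit and its adherence forms are already scheduled, and Protocol XIV times a 30-day safety evaluation from the last dose, so the stop date should be available; the SAP should name the field. The wording should be settled before unblinding.

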The process for titrating study medication at the initiation of study treatment and for maintaining them during the course of the study will be based on real or simulated plasma levels. To ensure local site blinding and standardization of measurements, some blood samples will be sent to a Central Laboratory for analysis. Lithium levels, TSH, T4, and creatinine will be analyzed by the Central Laboratory, while other samples, for complete blood count (CBC) and electrolytes will be sent to the local VA laboratories for analysis.

Lithium levels, creatinine, eGFR, and summary of side effects will be sent to the MAVERIC data coordinating center which will send real or simulated plasma levels and dosage adjustment recommendation to the Site Physician and to the Central Psychiatrist/Safety Officer. A lithium level of 1.2 or above will be considered a potentially dangerous situation and will be automatically sent to the Site Physician as well as the Coordinating Center and Central Psychiatrist/Safety Officer.

The Site Physician will use these levels and a check list review of symptoms at the time of the blood draw to make dose adjustments. During the initial dose adjustments, the Site Physician will typically decide between increasing doses by one pill per day, or maintaining the current dose.

Participants will have titration visits until they reach the target steady state: a serum lithium level between 0.6 and 0.8 mEq/L, over 2 consecutive visits, at the same dose, and with the second level the same or 0.1 mEq/L lower than the first level. It is expected that most patients will titrate within 4-6 visits, but the process may take fewer visits, or may take up to 8. If steady state is not achieved after 8 visits, the Central Psychiatrist/Safety Officer will work with the site on a case-by-case basis to determine a prescribing plan. If participants are not able to tolerate the dose needed to achieve the target level, they will be prescribed their maximum tolerated dose.

If it has been fewer than 60 days from randomization to achieving steady state, the participant's next visit will be a steady state follow-up visit 2 months after randomization (within the window allowed for steady state visits). If it takes more than 60 days, the next visit will be the 3 month steady state visit, and the month 2 visit will be omitted.

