4.3. Statistical Methods for Primary Efficacy Analysis

Primary efficacy analysis will include the modified intention to treat sample as defined in section 3.3 above.

The primary hypothesis can be stated as follows.

Under the null hypothesis: The 1-year event rate is 15% and the two treatment groups do not differ in their time to event hazard rates.

Under the alternative hypothesis: The 1-year event rate is 9.45% for patients treated with lithium and 15% for patients in the placebo group, resulting in an absolute reduction from 15% to 9.45% = 5.55% and a relative reduction of $(15 - 9.45)/15 = 37\%$. The group on lithium augmentation has a lower hazard rate than the placebo augmentation group with a hazard ratio for lithium therapy compared to control therapy lower than or equal to 0.61.

We will test this hypothesis with a two sided log rank test at 90% power and 4.8% Type I error (i.e., 5% overall error allows for one interim test at 0.2%). Null hypothesis will be rejected if the hazard ratio exceeds $1/0.61 = 1.64$ or falls below 0.61.

A significant difference showing that the lithium augmentation compared to placebo decreases the hazard of suicidal self-violence will be regarded as a positive result, whereas a result that shows lithium augmentation does not significantly differ from placebo or significantly increases the hazard rate relative to placebo will be regarded as a negative result.

Log rank test will be followed by Cox proportional hazards regression modeling to provide the hazard rates, their ratio and the 95% confidence interval about the ratio.

We will test the proportional hazards assumption by including a time*treatment interaction term in the model and use graphic methods to study goodness of fit as described in Anderson et. al., 1991.

The SAS code for the primary analysis is as follows, where, tx is coded as {1=lithium, 0=placebo}, event is coded as {1=adjudicated outcome, 0=otherwise}, and FUdays is counting number of days from randomization date to the first occurrence of (adjudicated outcome, death, 12 month date, or last study visit/contact date).

Log-Rank Test:

```
title "Survival Estimates by Month";
proc lifetest data=endpt plots=(s); time FUdays*event(0); strata tx; run;
quit;
proc lifetest data=endpt method=life plots=(ls) intervals=30 90 120 150
180 210 240 270 300 330 365; time FUdays*event(0); strata tx; run; quit;

title "Survival Estimates by Month";

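### Per-protocol membership depends on steady-state adherence, but follow-up is counted from randomisation, so participants whose early event ends treatment drop out of the per-protocol sample selectively

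*SAP*

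**What the plan says.** SAP 3.4 gives two routes into the per-protocol sample, both tied to the steady-state period.

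- Method 1, pill count, both arms: those with at least 80% "overall adherence during the steady state follow up period will be considered adherent to the protocol".
- Method 2, serum level, lithium arm only: those who reach target in titration and stay within 0.5-0.9 meq/liter "during the entire steady state follow up period will be considered adherent to the protocol".

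Lithium participants "adherent to the protocol based on either of the two methods will be considered as adherent"; placebo participants have the pill count only.

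SAP 4.5(2) repeats the primary efficacy analysis on the per-protocol "sample with adherence as defined in section 3.4 to evaluate efficacy among those adherent to the protocol". The clock is the one in SAP 4.3: "FUdays is counting number of days from randomization date to the first occurrence of" adjudicated outcome, death, 12 months or last contact. No landmark, delayed entry or rule for events before steady state is given.

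Titration is long in both documents. SAP 3.2 has "Titration visits will occur at intervals of 5-7 days over 3 months". Protocol XIII (Titrating study medication) says "It is expected that most patients will titrate within 4-6 visits, but the process may take fewer visits, or may take up to 8", and Protocol XIV (Titration Visits) spaces those visits 10 to 14 days apart. That is about 40-84 days for 4-6 visits and up to 112 days for 8.

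**The concern.** Membership is settled by what happens after titration, while the risk period begins before it. Someone who dies, withdraws or stops study drug during titration has no steady-state adherence and cannot be a member. Where an event led to that exit, the event leaves the sample with the participant. Those who stay bring their titration days as time at risk. For participants who have an early event and do go on to qualify, pill counts taken after the outcome decide whether the outcome is counted.

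Two things are at stake. The per-protocol event rates would be too low. If the share of early-event participants removed differs by arm, the per-protocol hazard ratio would also be shifted even with no drug effect. The analysis is meant to describe efficacy in adherent participants, and as written it cannot do that cleanly.

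**Working it through.** **Plan's own figure.** Inputs from SAP 4.3 and 10: one-year rates 15% and 9.45%, 745 evaluable per arm, two-sided alpha 0.048. The hazards are -ln(0.85) = 0.1625 and -ln(0.9055) = 0.0993, so HR = 0.611. Events = 745 x (0.15 + 0.0945) = 182. Freedman power is 90.0%, which matches the plan. (Schoenfeld gives 91.1%.) The documents give no figure for the per-protocol analysis.

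**Events in titration**, constant hazards, 745 x (1 - exp(-h x days/365.25)):

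| | Placebo | Lithium | Total | Share of 182 |
|---|---|---|---|---|
| First 60 days | 19.6 | 12.1 | 31.7 | 17% |
| First 90 days | 29.2 | 18.0 | 47.2 | 26% |

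**Events that by themselves bar membership.** Protocol II gives one-year suicide rates of 0.44-0.80% in VA attempt survivors. For 1,490 people that is 1490 x 0.0044 x 60/365.25 = 1.1 to 1490 x 0.0080 x 90/365.25 = 2.9 suicides during titration.

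**Equal removal in both arms.** Let e be the proportion with an event in titration and q the fraction of them removed, relative to other participants. The per-protocol rate is (p - qe)/(1 - qe).

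- Placebo, 90 days, e = 29.2/745 = 0.0393: q = 1 gives 11.5% and q = 0.5 gives 13.3%, instead of 15%.
- Lithium, 90 days, e = 18.0/745 = 0.0242: q = 1 gives 7.2%, instead of 9.45%.
- The HR stays at 1.00 under no effect and 0.61 under the design effect.

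**Unequal removal.** Large-sample Cox HR for assumed fractions qL (lithium) and qP (placebo):

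| qL / qP | True HR 1.00, 60 days | True HR 1.00, 90 days | True HR 0.61, 90 days |
|---|---|---|---|
| 0.50 / 0.25 | 0.95 | 0.93 | 0.57 |
| 0.75 / 0.25 | 0.91 | 0.86 | 0.53 |
| 1 / 0 | 0.83 | 0.74 | 0.45 |
| 0.50 / 1 | 1.11 | 1.18 | 0.72 |

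**Unequal titration length.** Simulation with no drug effect and a true rate of 15% in both arms. Assumptions: drug stopped by 40-80% of those with an event in titration and by 12% of the others; 75% of the rest adherent; log-normal time to steady state (sigma 0.3); hazard constant or front-loaded (Weibull shape 0.7). The per-protocol rate falls to about 11-14%. The HR is about 1.00 with equal titration, 0.95-0.99 if the lithium median is 15 days longer (75 vs 60), and 0.91-0.98 if 30 days longer (80 vs 50). Delayed entry at steady state returns 0.99-1.01.

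**Is event-driven stopping realistic?** Protocol VII reports one-year discontinuation in the earlier placebo-controlled lithium trial of 57.1% of 84 and 59.0% of 83 (48 + 49 = 97 people), and 50% (about 83-84 of 167) once suicide-related stops are excluded. The difference is about 13-14 stops against 17 events, or roughly 80%. This is only suggestive: the 50% is rounded, it covers the whole year, and that trial did not keep participants on after stopping drug.

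**After a landmark.** Even if all 1,490 were per-protocol, 182 - 32 = 150 events remain after day 60 (Schoenfeld power 85% at alpha 0.048) and 182 - 47 = 135 after day 90 (81%). The real sample would be smaller.

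**The case against.** A reader might infer that titration is immortal time in the strict sense. The documents do not support that. Most primary events are non-fatal. SAP 2 counts events after the first, and Protocol XIV says that stopping drug does not automatically mean withdrawal. A participant can have an event in titration, reach steady state, qualify, and enter with that event counted. Only the 1-3 expected suicides bar membership by themselves. Other removals depend on what follows the event, and the documents give no rate for that in this trial.

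A reader might also infer that the per-protocol HR is biased in favour of lithium. That needs an arm difference that the documents do not report and that the design works against. Under Protocol XIII, simulated placebo levels are adjusted for side effects and non-adherence and varied at random, and the biostatistician compares real with simulated distributions and revises the parameters if they diverge. Blinded Site Physicians titrate both arms. The 30-day scenario is also stretched: a lithium median of 80 days leaves 35% still titrating at day 90 and 13% beyond 112 days. The shifts are small against noise as well. With all 182 events, SE(log HR) = 2/sqrt(182) = 0.148, so an HR of 0.91 is 0.094/0.148 = 0.64 SE.

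Finally, this is one of three sensitivity analyses, and the minimum report content in SAP 11 names section 4.3 but not 4.5.

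These arguments limit the label, the size and the importance of the point. They do not remove the mismatch between the membership window and the clock, or the use of adherence after the outcome to decide who is counted.

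**Conclusion.** The point holds as selective removal of early events, with membership partly decided after the outcome. Between 17% and 26% of first events fall in the period concerned, at the design rates and with constant hazards. Per-protocol event rates are understated to the extent that early events lead to stopping: about 11-14% instead of 15% if 40-80% of those participants stop.

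Bias in the HR is conditional. There is none with equal removal. With no drug effect the HR is about 0.91-0.99 if titration is 15-30 days longer on lithium, and above 1 if removal is heavier on placebo. Those differences are assumptions. The two routes to membership on lithium against one on placebo make unequal removal plausible, but the direction cannot be fixed from the documents.

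Only sensitivity analysis (2) is affected; the size, power and alpha of the intention-to-treat analysis are not. This is a cheap improvement, not a threat to the trial's conclusion.

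**What to change.** In SAP 4.5(2), start the per-protocol analysis at a common fixed-day landmark at the end of titration, for example day 90. The alternative is delayed entry at each participant's first steady-state visit, which is an entry-time option in the existing PHREG call. Include only participants who are event-free and in follow-up at that time. The landmark is simpler, because a personal steady-state date is poorly defined for participants who never reach target. Before fixing the day, reconcile the titration visit intervals in SAP 3.2 (5-7 days) and Protocol XIV (10-14 days).

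In SAP 3.4, use the same pill-count rule in both arms, preferably on data before the landmark. With adherence judged after the landmark or entry date, some conditioning on later behaviour remains.

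Do not repair this by cutting Method 2 off at the first event. A participant with an event would then have fewer levels to keep in range, in the lithium arm only. Under no drug effect, with equal titration and delayed entry, that truncation gave an HR of 1.02-1.11 in simulation, against about 1.00 without it. The assumptions were that 50-80% reach target, 80-90% of levels are in range per visit, and 60-75% are adherent by pill count.

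Cost: SAP wording and a small code change. The estimate no longer covers titration and rests on fewer events, at most about 150 after day 60 or 135 after day 90. Judging adherence before the landmark also moves its meaning from steady state towards titration, which the SAP should state.
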